7.4 Study Agent (Cetuximab)

Cetuximab is an anti-EGFR receptor humanized chimeric monoclonal antibody. It is supplied as 100 mg/50 mL, single-use vial or a 200 mg/100 mL, single-use vial. For more information on this agent, refer to the FDA approved Package Insert.

7.4.1 Dose Calculation

Doses will be calculated on day 1 of each cycle using the patient's actual weight in the determination of body surface area. A variance of 10% of the calculated total dose will be allowed.

BSA (m²) =

$$\sqrt{\frac{(height) \times (weight)}{3131}}$$

For the determination of body surface area, height is measured in inches and weight is measured in pounds.

7.4.2 Treatment Administration

During neoadjuvant cetuximab, the initial dose is 400 mg/m² administered as a 120 minute intravenous infusion (maximum infusion rate 10 mg/min). The subsequent weekly doses are 250 mg/m² infused over 60 minutes (maximum infusion rate 10 mg/min). If a weight change of $\geq 10\%$ occurs, the cetuximab dose should be adjusted.

During radiation therapy, weekly dose is 250 mg/m² infused over 60 minutes (maximum infusion rate 10 mg/min) for the duration of radiation therapy (6–7 weeks). If a weight change of $\geq 10\%$ occurs, the cetuximab dose should be adjusted.

Cetuximab should not be delivered as an intravenous push or bolus. Administer via infusion pump or syringe pump. Do not exceed an infusion rate of 10 mg/min. Administer through a low protein binding 0.22-micrometer in-line filter. Parenteral drug products should be inspected visually for particulate matter and discoloration prior to administration, whenever solution and container permit. The solution should be clear and colorless and may contain a small amount of easily visible, white, amorphous, cetuximab particulates. Do not shake or dilute.

7.4.3 Dose Modifications or Escalations

7.4.3.1 Infusion Reactions

Serious infusion reactions occurred with the administration of Erbitux in approximately 3% of patients in clinical trials, with fatal outcome reported in less than 1 in 1000. Reduce the infusion rate by 50% for NCI CTCAE Grade 1 or 2 and non-serious NCI CTCAE Grades 3–4 infusion reactions. Once the infusion rate has been decreased due to an infusion reaction, it will remain decreased for all subsequent infusions. If the subject has a second infusion reaction with the slower infusion rate, the infusion should be stopped, and the subject should receive no further cetuximab treatment. Immediately and permanently discontinue cetuximab for serious infusion reactions, requiring medical intervention and/or hospitalization. All patients will be premedicated with diphenhydramine hydrochloride, 50 mg, (or an equivalent antihistamine) by *i.v.* 30–60 minutes prior to the first dose of cetuximab in an effort to prevent an infusion reaction. At the discretion of the treating physician, dexamethasone, 20 mg, and an H2 blocker also may be administered.

Serious infusion reactions, requiring medical intervention and immediate, permanent

discontinuation of cetuximab included rapid onset of airway obstruction (bronchospasm, stridor, hoarseness), hypotension, shock, loss of consciousness, myocardial infarction, and/or cardiac arrest. Severe (NCI CTCAE Grades 3 and 4) infusion reactions occurred in 2–5% of 1373 patients in clinical trials, with fatal outcome in 1 patient. Approximately 90% of severe infusion reactions occurred with the first infusion despite premedication with antihistamines.

Monitor patients for 1 hour following Erbitux infusions in a setting with resuscitation equipment and other agents necessary to treat anaphylaxis (eg, epinephrine, corticosteroids, intravenous antihistamines, bronchodilators, and oxygen). Monitor longer to confirm resolution of the event in patients requiring treatment for infusion reactions. Immediately and permanently discontinue Erbitux in patients with serious infusion reactions.

Infusion reactions may be managed per the following table:

| Adverse Event Grade | Treatment Guidelines |
|--|--|
| Grade 1: Transient flushing or rash; drug fever < 38° C (< 100° F) | For mild infusion reactions manifesting only as delayed drug fever, consider administering prophylactic antihistamine medications for subsequent doses. Maintain the cetuximab dose, but slow the infusion rate by 50%. Acetaminophen or a non-steroidal anti-inflammatory drug (NSAID) may be administered prior to subsequent cetuximab infusions, if not otherwise contraindicated in subjects. |
| Grade 2: Rash; flushing; urticaria; dyspnea; drug fever ≥ 38 C (≥ 100° F) | For moderate infusion reactions manifesting only as delayed drug fever, slow the infusion rate for cetuximab by 50% and consider administering antihistamine medications and/or steroid medications. Maintain the cetuximab dose. Acetaminophen or a non-steroidal anti-inflammatory drug (NSAID) may be administered prior to subsequent cetuximab infusions, if not otherwise contraindicated in subjects. |
| Grade 3: Symptomatic bronchospasm with or without urticaria; parenteral medication(s) indicated; allergy related edema/angioedema; hypotension | Severe infusion reactions require immediate interruption of cetuximab infusion and permanent discontinuation from further treatment with cetuximab. Appropriate medical therapy including epinephrine, corticosteroids, diphenhydramine, bronchodilators, and oxygen should be available for use in the treatment of such reactions. Subjects should be carefully observed until the complete resolution of all signs and symptoms. |
| Grade 4: Anaphylaxis | NO FURTHER STUDY DRUG THERAPY. Life threatening infusion reactions require immediate interruption of cetuximab infusion and permanent discontinuation from further treatment with cetuximab. Appropriate medical therapy including epinephrine, corticosteroids, diphenhydramine, bronchodilators, |

and oxygen should be available for use in the treatment of such reactions. Subjects should be carefully observed until the complete resolution of all signs and symptoms.

7.4.3.2 Rash: Dermatologic toxicities, including acneform rash, skin drying and fissuring, paronychial inflammation, infectious sequelae (for example *S. aureus* sepsis, abscess formation, cellulitis, blepharitis, conjunctivitis, keratitis, cheilitis), and hypertrichosis occurred in patients receiving Erbitux therapy. Acneform rash occurred in 76–88% of 1373 patients receiving Erbitux in clinical trials. Severe acneform rash occurred in 1–17% of patients.

Acneform rash usually developed within the first two weeks of therapy and resolved in a majority of the patients after cessation of treatment, although in nearly half, the event continued beyond 28 days. Monitor patients receiving Erbitux for dermatologic toxicities and infectious sequelae. Instruct patients to limit sun exposure during Erbitux therapy.

Rash occurring outside the radiation field may be graded according to the following table from CTCAE 4.0:

| | 1 | 2 | 3 | 4 |
|----------------------------|---|---|---|--|
| Pruritus/itching | Mild or localized; topical intervention indicated | Intense or widespread; intermittent; skin changes from scratching (e.g., edema, papulation, excoriations, lichenification, oozing/crusts); oral intervention indicated; limiting instrumental ADL | Intense or widespread; constant; limiting self care ADL or sleep; oral corticosteroid or immunosuppressive therapy indicated | - |
| Purpura | Combined area of lesions covering <10% BSA | Combined area of lesions covering 10 - 30% BSA; bleeding with trauma | Combined area of lesions covering >30% BSA; spontaneous bleeding | |
| Rash/acne/acneiform | Papules and/or pustules covering <10% BSA, which may or may not be associated with symptoms of pruritus or tenderness | Papules and/or pustules covering 10 - 30% BSA, which may or may not be associated with symptoms of pruritus or tenderness; associated with psychosocial impact; limiting instrumental ADL | Papules and/or pustules covering >30% BSA, which may or may not be associated with symptoms of pruritus or tenderness; limiting self care ADL; associated with local superinfection with oral antibiotics indicated | Papules and/or pustules covering any % BSA, which may or may not be associated with symptoms of pruritus or tenderness and are associated with extensive superinfection with IV antibiotics indicated; life-threatening consequences |
| Rash/maculo-papular | Macules/papules covering <10% BSA with or without symptoms (e.g., pruritus, burning, tightness) | Macules/papules covering 10 - 30% BSA with or without symptoms (e.g., pruritus, burning, tightness); limiting instrumental ADL | Macules/papules covering >30% BSA with or without associated symptoms; limiting self care ADL | - |
| Nail discoloration | Asymptomatic; clinical or diagnostic observations only; intervention not indicated | - | - | - |
| Nail loss | Asymptomatic separation of the nail bed from the nail plate or nail loss | Symptomatic separation of the nail bed from the nail plate or nail loss; limiting instrumental ADL | - | - |
| Nail ridging | Asymptomatic; clinical or diagnostic observations only; intervention not indicated | - | - | - |

Rash occurring inside the radiation field may be graded according to the following table from CTCAE 4.0:

| | 1 | 2 | 3 | 4 |
|---|------------------------------------|--|--|--|
| Dermatitis associated with radiation | Faint erythema or dry desquamation | Moderate to brisk erythema; patchy moist desquamation, mostly confined to skin folds and creases; moderate edema | Moist desquamation other than skin folds and creases; bleeding induced by minor trauma or abrasion | Life-threatening consequences; skin necrosis or ulceration of full thickness dermis; spontaneous bleeding from involved site; skin graft indicated |

Cetuximab dose should be modified per the following table in case of severe (grade 3 / 4) rash:

| Occurrence of severe (grade 3/4) acneform rash | Cetuximab modification |
|--|---|
| 1 st occurrence | Delay infusion 1 to 2 weeks. If there is improvement, continue cetuximab at at 250 mg/m ² . If there is no improvement, discontinue cetuximab. |
| 2 nd occurrence | Delay infusion 1 to 2 weeks. If there is improvement, continue cetuximab at at 200 mg/m ² . If there is no improvement, discontinue cetuximab. |
| 3 rd occurrence | Delay infusion 1 to 2 weeks. If there is improvement, continue cetuximab at at 150 mg/m ² . If there is no improvement, discontinue cetuximab. |
| 4 th occurrence | Discontinue cetuximab |

7.4.3.3 Dose modifications for other toxicity: due to lack of evidence that cetuximab contributes to these toxicities, cetuximab dose will not be altered for renal failure, fatigue, nausea/vomiting.

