12.2 Commercial Agents

Product description: Cetuximab is commercially available from Merck, IMCLONE. In this protocol cetuximab is not supplied, and is paid for by the patient or his insurance company.

Preparation: Erbitux® (cetuximab) is supplied at a concentration of 2 mg/mL as a 100 mg/50 mL, single-use vial or as a 200 mg/100 mL, single-use vial as a sterile, preservative-free, injectable liquid. It should be prepared as for standard preparation as per the package insert. Store vials under refrigeration at 2° C to 8° C (36° F to 46° F). **Do not freeze.** Increased particulate formation may occur at temperatures at or below 0° C. This product contains no preservatives. Preparations of Erbitux in infusion containers are chemically and physically stable for up to 12 hours at 2° C to 8° C (36° F to 46° F) and up to 8 hours at controlled room temperature (20° C to 25° C; 68° F to 77° F). Discard any remaining solution in the infusion container after 8 hours at controlled room temperature or after 12 hours at 2° C to 8° C. Discard any unused portion of the vial.

Route of administration:

- Premedicate with an H1 antagonist (eg, 50 mg of diphenhydramine) intravenously 30–60 minutes prior to the first dose; premedication should be administered for subsequent Erbitux doses based upon clinical judgment and presence/severity of prior infusion reactions.
- Administer 400 mg/m² initial dose as a 120-minute intravenous infusion followed by 250 mg/m² weekly infused over 60 minutes.
- Reduce the infusion rate by 50% for NCI CTCAE Grade 1 or 2 infusion reactions and non-serious NCI CTCAE Grades 3–4 infusion reactions.
- Permanently discontinue for serious infusion reactions. Withhold infusion for severe, persistent acneform rash. Reduce dose for recurrent, severe rash.

Expected toxicities: The most common adverse reactions (incidence $\geq 25\%$) are: cutaneous adverse reactions (including rash, pruritus, and nail changes), headache, diarrhea, and infection. Refer to the package insert for a complete list of toxicities.

Drug Interactions: No known drug interactions with cetuximab.

13. Data Collection and Records to be Kept

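### For non-serious Grade 3–4 cetuximab infusion reactions, the prose of Section 7.4.3.1 and Section 12.2 continue the drug at half rate, while the table in 7.4.3.1 stops it permanently

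*Combined protocol and SAP*

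**What the plan says.** Section 7.4.3.1 handles infusion reactions twice, first in prose and then in a table.

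The prose divides Grade 3–4 reactions by seriousness. For the non-serious ones it says: "Reduce the infusion rate by 50% for NCI CTCAE Grade 1 or 2 and non-serious NCI CTCAE Grades 3–4 infusion reactions". It adds: "Once the infusion rate has been decreased due to an infusion reaction, it will remain decreased for all subsequent infusions". For the others it says: "Immediately and permanently discontinue cetuximab for serious infusion reactions, requiring medical intervention and/or hospitalization". Section 12.2 gives the same split: "Reduce the infusion rate by 50% for NCI CTCAE Grade 1 or 2 infusion reactions and non-serious NCI CTCAE Grades 3–4 infusion reactions", with permanent discontinuation kept for serious reactions.

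The table divides by grade alone. Its Grade 3 row reads "Severe infusion reactions require immediate interruption of cetuximab infusion and permanent discontinuation from further treatment with cetuximab". Its Grade 4 row opens with "NO FURTHER STUDY DRUG THERAPY" and likewise calls for permanent discontinuation. Neither row mentions seriousness.

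**The concern.** A site that follows the prose or Section 12.2 would give another infusion to a patient whom the table takes off the drug for good. This is a stop-or-continue safety rule for a type of reaction that Section 7.4.3.1 says has been fatal. The section also says that roughly 90% of severe reactions come with the first infusion, which in this trial is the first neoadjuvant dose. The rule would therefore usually be needed at the very start of treatment, before any decision about what to give with radiation. Section 3 plans clinical activity at two institutions, so two patients with the same reaction could be managed in opposite ways, each in line with some part of the protocol.

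**Working it through.** The question is one of text, so the passages are set side by side. The only arithmetic is a bound on the number of patients.

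**Step 1. Does halving the rate mean continuing the drug?** Yes. The prose carries the reduced rate forward to later infusions ("Once the infusion rate has been decreased due to an infusion reaction, it will remain decreased for all subsequent infusions"), so further doses are foreseen.

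**Step 2. Can the Grade 3 row be read as covering only serious reactions?** No. The row uses the word *severe*, and the prose ties that word to grade: "Severe (NCI CTCAE Grades 3 and 4) infusion reactions occurred in 2–5% of 1373 patients in clinical trials". The rows are also labelled by grade.

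**Step 3. Compare the instructions by category.**

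| Reaction | Prose of 7.4.3.1, and 12.2 | Table in 7.4.3.1 | Agree? |
|---|---|---|---|
| Grade 1–2 | Half rate, continue | Half rate, continue (worded for reactions showing only as delayed drug fever) | Essentially |
| Grade 3–4, serious | Stop permanently | Stop permanently | Yes |
| Grade 3–4, non-serious | Half rate, continue | Stop permanently | **No** |

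The contradiction lies in the last row only.

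**Step 4. How wide is that row?** The table describes Grade 3 as "Symptomatic bronchospasm with or without urticaria; parenteral medication(s) indicated; allergy related edema/angioedema; hypotension" and Grade 4 as anaphylaxis. Bronchospasm and hypotension also appear among the prose's examples of serious reactions. A reaction that calls for parenteral medication, or anaphylaxis, plausibly meets the prose criterion of needing medical intervention. For these, both parts stop the drug. Allergy-related edema or angioedema is a Grade 3 descriptor in the table but is not among the prose's examples. A patient with that reaction and no clear need for intervention could be read either way.

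**Step 5. Upper bound on the number affected.** Inputs: 27 planned patients (Section 16.2) and a 2–5% rate for all Grade 3–4 reactions (Section 7.4.3.1).

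- 27 × 0.02 = 0.54
- 27 × 0.05 = 1.35

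These counts include serious reactions, on which the passages agree, so the number in the disputed row can only be smaller. The protocol gives no rate for non-serious Grade 3–4 reactions.

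**Step 6. What follows for the treatment path?** Section 7.2.5 assigns patients by CT response and by folliculitis arising at any time between the first cetuximab dose and the start of radiation. It does not require all three neoadjuvant doses. Permanent discontinuation does bear on Section 7.2.6, under which responders receive weekly cetuximab throughout radiation unless it is stopped for toxicity.

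**The case against.** The strongest reply is that the disputed category is nearly empty. Section 7.4.3.1 supplies both a criterion and examples for *serious*, and most of the table's Grade 3 descriptors, as well as anaphylaxis, fit them. The same section puts serious reactions at approximately 3%. If those are assumed to lie wholly within the 2–5% that are severe, the remainder is at most 5% − 3% = 2%, or 27 × 0.02 = 0.54 of a patient, and could be zero. This stands as a limit on size, subject to that assumption, which the protocol does not state. It does not remove the contradiction, because the protocol names the category in two places and gives it an instruction that the table reverses. The terms are not aligned elsewhere either. Section 8.2 counts any life-threatening event as serious and the table calls Grade 4 life-threatening, so under 8.2 a non-serious Grade 4 reaction could not exist, yet 7.4.3.1 and 12.2 provide for one.

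A second reply is that the table is only guidance: it is introduced with *may*, and the two prose passages agree with each other. That has some weight, but the Grade 3 and Grade 4 rows themselves use *require*, and no order of precedence is given. An optional table would leave sites free to choose between opposite actions.

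A reader might also infer three stronger things that the documents do not support.

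- *Every Grade 3–4 reaction receives opposite instructions.* Serious ones do not.
- *The conflict decides who is a responder.* Section 7.2.5 does not make completion of the three doses a condition, so a patient taken off the drug can still meet the responder definition.
- *One patient moving in or out of the 16 planned responders shifts two-year locoregional control by 1/16 = 6.25 percentage points.* That is the weight of one changed outcome with the denominator fixed. At the planned 75% (12/16), removing one patient gives 11/15 = 73.3% or 12/15 = 80.0%, a change of −1.7 or +5.0 points.

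**Conclusion.** The protocol contradicts itself. For a Grade 3–4 infusion reaction that is not serious by the prose criterion, the prose of 7.4.3.1 and Section 12.2 continue cetuximab at half rate, the table in 7.4.3.1 stops it permanently, and nothing settles which applies. The consequences are possible re-exposure after a severe reaction and uncertainty over whether cetuximab can be given with radiation.

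The number of patients is likely to be small: fewer than the 0.54 to 1.35 of 27 that corresponds to all Grade 3–4 reactions, with the exact figure not obtainable from the documents. The bound assumes that the quoted 2–5% applies to this population. The case for correction rests on opposite stop and continue instructions for a potentially fatal reaction, and not on an expected effect on the primary endpoint. No view is taken here on which instruction is right.

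**What to change.** The sponsor should reconcile three places: the prose of Section 7.4.3.1, the Grade 3 and Grade 4 rows of its table, and Section 12.2. After the change they should give one consistent instruction for Grade 3–4 infusion reactions and use *serious* and *severe* in the same sense throughout. The choice of rule belongs to the sponsor's medical lead. The cost is a wording amendment, with no added patients, visits or staff.

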7.4.3.4 Hematologic Toxicity

Cetuximab will not be dose reduced or held for hematologic adverse events, such as neutropenia, neutropenic fever, or thrombocytopenia.

7.4.3.5 Non-Hematologic Toxicity

See above

Cardiopulmonary Arrest

Cardiopulmonary arrest and/or sudden death occurred in 4 (2%) of 208 patients treated with radiation therapy and Erbitux as compared to none of 212 patients treated with radiation therapy alone in a randomized, controlled trial in patients with SCCHN. Three patients with prior history of coronary artery disease died at home, with myocardial infarction as the presumed cause of death. One of these patients had arrhythmia and one had congestive heart failure. Death occurred 27, 32, and 43 days after the last dose of Erbitux. One patient with no prior history of coronary artery disease died one day after the last dose of Erbitux. Carefully consider use of Erbitux in combination with radiation therapy in head and neck cancer patients with a history of coronary artery disease, congestive heart failure, or arrhythmias in light of these risks. Closely monitor serum electrolytes, including serum magnesium, potassium, and calcium, during and after Erbitux.

Pulmonary Toxicity

Interstitial lung disease (ILD), including 1 fatality, occurred in 4 of 1570 (<0.5%) patients receiving Erbitux in clinical trials. Interrupt Erbitux for acute onset or worsening of pulmonary symptoms. Permanently discontinue Erbitux for confirmed ILD.

Dermatologic Toxicity

Dermatologic toxicities, including acneform rash, skin drying and fissuring, paronychial inflammation, infectious sequelae (for example *S. aureus* sepsis, abscess formation, cellulitis, blepharitis, conjunctivitis, keratitis, cheilitis), and hypertrichosis occurred in patients receiving Erbitux therapy. Acneform rash occurred in 76–88% of 1373 patients receiving Erbitux in clinical trials. Severe acneform rash occurred in 1–17% of patients.

Acneform rash usually developed within the first two weeks of therapy and resolved in a majority of the patients after cessation of treatment, although in nearly half, the event continued beyond 28 days. Monitor patients receiving Erbitux for dermatologic toxicities and infectious sequelae. Instruct patients to limit sun exposure during Erbitux therapy.

Hypomagnesemia and Electrolyte Abnormalities

In patients evaluated during clinical trials, hypomagnesemia occurred in 55% of patients (199/365) receiving Erbitux and was severe (NCI CTCAE Grades 3 and 4) in 6–17%. The onset of hypomagnesemia and accompanying electrolyte abnormalities occurred days to months after initiation of Erbitux. Periodically monitor patients for hypomagnesemia,

hypocalcemia, and hypokalemia, during and for at least 8 weeks following the completion of Erbitux. Replete electrolytes as necessary.

7.4.4 Concomitant Medications

There are no concomitant medications that are contraindicated with cetuximab.

